2.3 Proliferation in Hyperplastic Benign Breast Tissue as a Response Endpoint

Women with diagnostic biopsy evidence of proliferative breast disease following an abnormal finding on physical exam or mammogram are at increased risk for breast cancer ranging from ~2 fold for hyperplasia without atypia to a 4-5 fold increase in relative risk for atypical ductal or lobular hyperplasia [Dupont 1985; Tavessoli 1990; Drystad 2015; Hartmann 2014]. However, women age 50-69 who simply have a diagnostic breast biopsy without evidence of proliferative breast disease or family history may also have a 20% up to a 2 fold increase in the risk for breast cancer [Drystad 2015; Castells 2015]. Proliferation as measured by detection of mitotic index and/or detection of nuclear associated proliferation antigens such as Ki-67 (MIB-1) progressively increases from normal to hyperplasia to atypical hyperplasia and DCIS [Shrestha 1992; Mommers 1999; Allred 1998].

In normal pre-menopausal breast epithelium, proliferation (Ki-67) correlates with systemic levels of progesterone, and is lowest in the follicular phase (0.2-0.7%) and highest in the luteal phase (~2%) [Soderqvist 1997; Shoker 1999]. Ki-67 labeling averages 0-1% in normal postmenopausal epithelium [Shoker 1999]. In diagnostic biopsies from proliferative breast disease Ki-67 has been reported to vary between 1 and 6% [Shaaban 2002; Allred 1998].

A Ki-67 labeling index of 2% or higher in usual duct hyperplasia (cross sectional study from Shaaban) or atypical hyperplasia (Mayo prospective cohort study Santisteban) is associated with increased risk of breast cancer compared with women with hyperplasia or atypical hyperplasia with lower levels of proliferation [Shaaban 2002; Santisteban 2010]. We have used random periareolar fine needle aspiration to obtain benign breast tissue from women at increased risk for breast cancer for risk stratification and to obtain tissue for Phase II prevention

trials for over 2 decades [[name] 2000, 2002, 2005, 2007, 2010, 2013]. Similar to diagnostic biopsy series, [Dupont 1985; Hartmann 2014] women with cytologic evidence of hyperplasia with atypia have an increased risk of DCIS and invasive cancer as well as a higher proliferative rate [[name] 2000; Khan 2005]. We observed a median Ki-67 labeling index of 1.4% in RPFNA samples exhibiting hyperplasia with or without atypia from high-risk post-menopausal women in whom there were sufficient cells for Ki-67 to be attempted [Khan 2005]. Inter- and intra-observer variation in interpretation of staining results was low with a Cronbach's alpha of 0.99 [Khan 2005].

A number of antihormonal treatments effective in breast cancer treatment and prevention have been shown to reduce proliferation indices in benign and cancerous breast epithelial cells by 17-50% relative to baseline. [Clarke 1993; Chang 2000; Dowsett 2001; Dowsett 2005; Decensi 2003]. Reduction in proliferation (Ki-67) at two weeks and 12 weeks in the neoadjuvant IMPACT Trial (tamoxifen, anastrozole, combination) was positively associated with disease free survival [Dowsett 2005]. Tamoxifen has been shown to reduce proliferation (Ki-67) in benign breast tissue of postmenopausal women [de Lima 2003]. In a single arm pilot trial six months of the aromatase inhibitor letrozole reduced proliferation by 66% in benign tissue from high-risk women despite continuing hormone replacement [[name] 2007].

Ki-67 is quantitative, exhibits low intra- and inter-observer variance, and is favorably modulated in benign breast tissue with agents known to be effective in primary and secondary breast cancer prevention. Consequently, change in proliferation as measured by Ki-67 immunohistochemistry is often used as a primary response endpoint in Phase II and pilot prevention studies of premenopausal women and postmenopausal women on hormone replacement therapy [[name] 2005; [name] 2007]. We and others have shown that random periareolar fine needle aspiration is accepted by high risk women and is a reproducible means to sample breast tissue [[name] 2000; Ibarra-Drendall 2009]. However, given the extent of lobular involution in definitively postmenopausal women not on hormone replacement therapy, a sizable number of women may need to be screened by RPFNA to detect those with a Ki-67 of 1-2% or higher, making reduction in Ki-67 an impractical endpoint for primary prevention trials in definitively postmenopausal women not on hormone replacement. Ki-67 has not been adequately studied in moderate to high risk peri-menopausal women < 60 having menopausal symptoms in order to determine the proportion of women with a Ki-67 of >1% in their RPFNA specimen.

2.4 Other Risk and Mechanism of Action Biomarkers in Benign Breast Tissue Likely to be Modulated by Duavee®

Sampling of benign breast tissue also provides the opportunity to assess fresh frozen tissue for assessment of change in gene or protein expression to better define mechanism of action. We will assess a number of estrogen response genes including ER alpha, progesterone receptor, pS2 (Trefoil factor 1) cMYC, GREB-1, amphiregulin, known to be increased by estrogen and antagonized by bazedoxifene in mice benign and malignant mammary tissue [Song 2012]. Several additional genes known to be increased at the mRNA level by estrogen such as amphiregulin, FOS, and JAK2 will also be assessed by RTqPCR [Chang 2010; [name] 2010; Phillips 2013; Ibarra-Drendall 2012; [name] 2013]. Reverse phase protein arrays will also be used to identify changes in proteins and phosphoproteins in pathways important in breast carcinogenesis [Akbari 2014; Meric-Bernstam 2014; [name] 2013].

2.5 Mammographic Breast Density as Risk and Response Biomarker

Mammographic density which is composed histologically of ductal and stromal tissue, and fluid is recognized as a risk factor for breast cancer particularly when corrected for age and Body Mass Index (BMI) [Boyd 1993; Boyd 1995; Boyd 1998; Byrne 1995; Warwick 2014]. Although absolute dense area along with % dense area are both risk biomarkers, % density appears to be the stronger risk biomarker [Pettersson 2014]. In a recent analysis, Boyd et al. suggest that women with a high density in the highest tertile of mammographic density corrected for BMI have a risk of 2.63x that of women in the lowest tertile (0-20% density), and women in the mid tertile (20-41%) a risk of 2.15X that of women in the lowest tertile [Boyd 2014]. Given these updated results it is reasonable to include women with an estimated breast density of 25% or higher in the risk criteria for consideration of participation in this study.

Change in mammographic density is validated as a surrogate response biomarkers for trials involving the selective estrogen receptor tamoxifen which is known to reduce risk for breast cancer by 40% or more [Cuzick 2011; Cuzick 2013]. However, change in breast density is not modulated by raloxifene, a selective estrogen receptor modulator known to reduce risk for breast cancer in postmenopausal women almost to the same extent as tamoxifen [Martino 2004; Freedman 2001; Pearman 2010]. Nor is density modulated with exemestane, an aromatase inhibitor that is shown to reduce breast cancer risk by 65%. [Cigler 2011; Goss 2011]. Weight reduction may actually increase percent dense area [[name] 2013; Boyd 1997]. Breast density, even with computer assisted calculations, is subjective and pre and post intervention assessments should be performed by the same individual at the same setting with the rater blinded as to which image was baseline [Stone 2003]. In addition there are a number of technical factors that can introduce error when change is being evaluated including variation in type of imaging, positioning and degree of compression.

Breast density (% dense area) was not significantly altered compared to controls over 24 months in a centrally read retrospective analysis of digital mammograms from the SMART 1 study which compared bazedoxifene + 0.45 mg CE or 0.625 mg CE vs placebo to placebo or 60 mg of raloxifene. (Mean reductions of 0.05-.41%). In a prospective cohort of over 900 women in the SMART 5 study ages 40-65 with a mean baseline density of ~25% there was no change in centrally read digital mammographic density over a 12 month period comparing 0.45 or 0.625 mg CE + 20 mg bazedoxifene vs placebo (both declined by ~ 0.3 %). A comparator of CE + medoxyprogesterone acetate increased by 1.66% [Pinkerton 2013]. Automated volumetric mammographic breast density assessments appear to have less variation than computer assisted operator density assessments [Eng 2014; Alonzo-Proulx 2015; Brand 2014; Ekpo 2014]. Automatic Volpara volumetric density measurements utilized in this study will be compared to the Cumulus % dense area to explore whether small changes in density with 6 months of Duavee® may be detected with the volumetric method.

2.6 Serum risk Biomarkers as Response Endpoints

Higher endogenous bioavailable estradiol and testosterone levels have long been associated with breast cancer risk in postmenopausal women [Toniolo 1994; Pearce 1989; Tworoger 2014; Verkasalo 2001; Missmer 2006; Farhat 2011]. Several serum biomarkers associated with metabolism are known to be risk biomarkers for proliferative breast disease and breast cancer in postmenopausal women including serum insulin, markers of insulin resistance such as HOMA-IR, adiponectin, leptin: adiponectin ratio [[name] 2012; Catsburg 2014; Gunter 2009; Hernandez 2014; Vona-Davis 2007]. Lipocalin 2 (Lcn2) and retinol binding protein 4 (RBP4) are

also increased in insulin resistance. Lipocalin 2 has been shown to promote breast cancer development and progression primarily through activation of the estrogen receptor in preclinical models [Guo 2012; Yang 2009; Shi 2008]. An increase in the serum ratio of retinol binding protein to STA6 is oncogenic and is mediated through the actions of JAK2 and Stat 3 and 5 at the cellular level [Berry 2014]. Treatment of ovariectomized mice with conjugated estrogen (CE), bazedoxifene (BZA) or the combination vs control suggests that both CEE and BZA alone or in combination have favorable effects on leptin, adiponectin, Lcn2, and RBP4. The most dramatic effects appear to be for the leptin: adiponectin ratio (reduced by over 10 fold in the ovariectomized mouse) [Kim 2014]. Ovariectomized mice subjected to 10-12 weeks of diets producing obesity showed attenuation of weight gain, fat mass gain, and measures of insulin resistance when treated with BZA and CE [Barrera 2014].

3. SUMMARY OF STUDY PLAN

Peri- or post-menopausal women meeting the risk and medical eligibility criteria (see below) will undergo random periareolar fine needle aspiration (RPFNA) under the umbrella screening protocol HSC 4601. Women with at least 500 cells on their cytomorphology and/or Ki-67 slide, but with Ki-67 expression less than 4% will be eligible to proceed to the intervention phase of this study. At a baseline on-study visit, women will have a physical exam, DEXA for body composition, complete a 29 item Menopause Quality of Life Intervention Questionnaire [Lewis 2005] and hot flash assessment, have fasting blood obtained for biomarkers as well as to assure reasonable normal organ function. Key symptoms assessed at baseline will be hot flashes. Forty women will be entered on the treatment portion of the trial and will take Duavee® one tablet daily. Drug will be supplied by Pfizer. After 6-8 months of study agent, biomarkers will be reassessed. Mammogram, DEXA for body composition, RPFNA, and blood draw will be repeated. A complete side effects assessment will be performed. Entry of 40 women should allow 36 women to complete the study and be evaluable for the primary endpoint. Trial accrual is anticipated to take 6 months with completion of clinical aspects of the study by 12 months. Since this is not a blinded study, analysis of feasibility and changes in Ki-67 can take place immediately.

4. PARTICIPANT SELECTION

4.1 Inclusion Criteria for Screening RPFNA

Note that the screening RPFNA may be conducted under a separate IRB-approved research protocol with its own consent form. Potential participants are not required to make a decision regarding participation in the Duavee® trial until after receipt of the results of their RPFNA. However, if a woman is undergoing an RPFNA expressly for participation for this protocol, the following should be kept in mind for eligibility

- 4.1.1 Women with vasomotor symptoms with a uterus who are postmenopausal (no menstrual period for 12 months) or in late menopause transition (no period for 3 months and elevated FSH) [Sherman 2005].
- 4.1.2 Age ≤65
- 4.1.3 BMI: <36 kg/m²
- 4.1.4 Breast Imaging: Class I-III mammogram within 6 months of RPFNA. If Class 0 or 4, must be resolved with additional procedures. If breast imaging pre and post study is performed at KUMC, then volumetric assessment by Volpara software will be performed.
- 4.1.5 If previously on oral contraceptives or hormone replacement, off for 8 weeks or more prior to baseline RPFNA. The exception is low dose vaginal hormones (estring, vagifem, or 0.5 gram or less of conjugated estrogen vaginal cream twice weekly or less often). These vaginal preparations may be continued at the same dose.
- 4.1.6 Risk Factors/Level. Moderate risk of developing breast cancer based on either by having at least one of following:
 - First or second degree relative with breast cancer age 60 or younger;
 - Prior breast biopsy;
 - Prior RPFNA atypia;
 - Estimated Mammographic Density of 25% or higher;
 - Gail 5-year risk of >1.7% (as calculated by the NCI Breast Cancer Risk Assessment Tool) or a 5 year Gail Risk of 2X that for age group; and/or
 - IBIS Breast Cancer Risk Evaluation (<http://www.ems-trials.org/riskevaluator/>) [Tyrer–Cuzick 2004]. 10-year relative risk of >2X that for the population for age group.

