1.2 Secondary Exploratory Objectives

A number of analyses will be conducted in an effort to document and describe the effects of Duavee® on a variety of variables that are actual or potential risk biomarkers for development of breast cancer.

- Assess benign breast tissue for decrease in Ki-67 in women with Ki-67 of 1% or higher
- Assess changes in benign breast tissue estrogen responsive genes by RTqPCR
- Assess changes in benign breast tissue peptides and phosphopeptides.
- Assess changes in serum bioavailable hormones and cytokines
- Assess change in bazedoxifene serum levels as a function of BMI, percent body fat, and compliance (by tablet count)
- Document change if any in body composition (DEXA), and waist circumference
- Document change if any in volumetric breast density (Volpara) and compare to % dense area (Cumulus)

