4.2.3 Medications

- Current anticoagulant use (must discontinue for 3 weeks prior to FNA)
- Taking systemic hormones within two months (eight weeks) prior to screening RPFNA.
- Taken tamoxifen, raloxifene, or an aromatase inhibitor within the past 6 months
- Participation on any chemoprevention trial within 6 months

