4.3 Inclusion Criteria for Intervention Phase

4.3.1 RPFNA Results: An RPFNA performed less than six months prior to enrollment on study that exhibits at least 500 cells on the cytology or Ki-67 slide, and a Ki-67 positivity measured on at least 500 cells that is less than 4%.

4.3.2 Baseline chemistry profile showing reasonably normal renal and hepatic function. Creatinine <2.0, Bilirubin < 2.5, and albumin > 3.4

4.3.3 Willingness to comply with study procedures.

- Willing to have a blood draw for serum to archive bioavailable estradiol, SHBG, FSH, and bazedoxifene levels as well as a chemistry profile to ensure reasonable normal organ function at baseline and 6 month visits (approximately four tubes of blood collected)
- Willing to have a DEXA scan for body composition and waist measurement at baseline and 6-8 months.
- Willing to have a repeat mammogram and RPFNA at 6-8 months following initiation of study drug
- Willing to undergo a history, physical, vitals and breast exam at baseline and 6 month visits
- Willing to be contacted by the trial coordinator at months 1 and 3 during the 6 month study period.
- Willing to complete a 29 item validated Menopause Quality of Life Intervention Questionnaire and hot flash assessment at baseline and 6 month visits
- Willing to sign and able to understand separate consents for the RPFNAs and for study participation

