7.2.2 Pre-study risk assessment

- Gail Risk assessment: A 5-year projected probability of breast cancer development ("Gail risk") will be calculated using the NCI website algorithm (<http://www.cancer.gov/bcrisktoolmobile>). The risk is expressed as relative to the average risk for women in the same age-group, based on values calculated from the Surveillance, Epidemiology, and End Results (SEER) Program provided by the NCI (<http://srab.cancer.gov/devcan/>)
- IBIS Risk assessment: a 10 year The IBIS Risk Assessment will be performed. The IBIS Breast Cancer Risk Evaluation Tool can be found (<http://www.ems-trials.org/riskevaluator/>).
- Mammographic Density Estimation: Mammographic Density will be estimated from the pre-study digital mammogram left cranial caudal view. Note that a digital mammogram must have been performed within 6 months of RPFNA.

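### The hormone washout is counted from the RPFNA and not from the baseline mammogram, so baseline density can be an on-hormone or long pre-treatment reading and its later fall be read as change with Duavee

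*Combined protocol and SAP*

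**What the plan says.** All the timing rules for hormones sit in the screening criteria for the RPFNA. Section 4.1.5 reads "If previously on oral contraceptives or hormone replacement, off for 8 weeks or more prior to baseline RPFNA", with an exception for low-dose vaginal products. Section 4.2.3 excludes systemic hormones in the eight weeks before the screening RPFNA. Section 4.2.2 repeats the 8 weeks without naming another anchor.

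The mammogram has its own, looser window. Section 4.1.4 asks for a "Class I-III mammogram within 6 months of RPFNA". Section 7.2.2 repeats the window ("Note that a digital mammogram must have been performed within 6 months of RPFNA") and makes that image the source of density: "Mammographic Density will be estimated from the pre-study digital mammogram left cranial caudal view". The Schedule of Events (7.1) has no other mammogram before treatment.

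Section 4.3.1 then allows "An RPFNA performed less than six months prior to enrollment on study". Treatment lasts 6 months, with up to two more for scheduling (7.4).

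Change in density by Volpara, compared with Cumulus % dense area, is the last of the exploratory objectives in 1.2. Section 13.4 analyses it as a paired change from baseline, by paired t-test or signed-rank test, at p<0.05 without adjustment. Section 13.5 includes every evaluable pair. Its only supporting analysis is restricted on compliance and on exposure to Duavee. There is no control arm (5.1).

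**The concern.** A baseline for a drug comparison should be read under the conditions in which the drug is started. For Ki-67 the plan secures this by putting the washout on the aspirate. For density it does not, because the image can be months older than the aspirate.

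Take a woman who stopped combined hormone therapy 9 weeks before the RPFNA and had her mammogram 4 months before it. She meets every rule, and her baseline density is an on-hormone reading. The Schema's statement that participants are not on systemic hormone replacement describes them at entry, not on the day of the mammogram. Such women are foreseeable: 4.1.5 is written for prior hormone users, and the trial recruits women with vasomotor symptoms.

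The long allowable gap before the first tablet adds a second source of change that is not due to the drug. By contrast, DEXA must fall within 90 days before study initiation (7.2.3.2), and bloods are drawn at the baseline visit (7.1).

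Both sources push density down, which is the direction of an apparent benefit. With one arm and no rule on hormone status or interval, the analysis cannot separate either from an effect of Duavee.

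**Working it through.** The plan gives no power, sample size or target effect for density, so there is no figure of its own to reproduce. The checks below use its windows and the density figures in 2.5.

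**Inputs**
- Mammogram window: 6 months (about 26 weeks) before the RPFNA (4.1.4, 7.2.2).
- Hormone washout: 8 weeks before the RPFNA (4.1.5, 4.2.3).
- RPFNA to enrolment: just under 6 months at most (4.3.1).
- Time on drug: 6 to 8 months (7.4).
- From 2.5, over 12 months: "A comparator of CE + medoxyprogesterone acetate increased by 1.66" per cent; bazedoxifene/CE and placebo each fell by about 0.3%.
- From 2.5, the 24-month retrospective bazedoxifene/CE study: mean reductions of 0.05 to 0.41%, not significantly different from controls.

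**1. Part of the window in which the image can be on-hormone**
For a woman who stopped s weeks before the RPFNA (s at least 8), this is 26 - s weeks.
- s = 8: 26 - 8 = 18 weeks, or 18/26 = 69% of the window.
- s = 20: 26 - 20 = 6 weeks.

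So 18 weeks is the maximum. It describes the window and is not a probability.

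**2. Intervals**
- Baseline mammogram to first tablet: up to 6 + 6 = about 12 months.
- Between mammograms: from 6 months to 6 + 6 + 8 = about 20 months, for 6 to 8 months of drug.

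**3. Shift in mean change from on-hormone baselines**
Shift = f × d, where f is the share of density pairs with an on-hormone baseline (an assumption; the documents give none) and d is the excess fall in each such pair. Assume prior combined therapy and full reversal. Then d is 1.66 points, or 1.66 + 0.3 = 1.96 points against the untreated course.

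| f | d = 1.66 | d = 1.96 |
|---|---|---|
| 10% | -0.17 | -0.20 |
| 20% | -0.33 | -0.39 |
| 30% | -0.50 | -0.59 |

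A spurious fall of 0.3 points needs f = 0.3/1.96 = 15% (or 0.3/1.66 = 18%).

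**4. Untreated decline**
At the plan's placebo rate, taken as linear, decline is 0.3 × months/12.
- Before the first tablet, at the 12-month maximum: 0.3 × 12/12 = 0.3 points.
- Between images: 0.3 × 6/12 = 0.15 points at 6 months and 0.3 × 20/12 = 0.5 points at 20 months.

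This part needs no assumption about prior hormone use.

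**5. Effect on the test**
Assume no drug effect, a two-sided paired t-test at 0.05 (the plan states no sidedness), d = 1.96, and an SD of change of 2 to 5 points (an assumption). The number of density pairs is unknown, because both images must be at KUMC, so two values are shown. The chance of p<0.05 is then:

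| Pairs | f = 10% | f = 25% |
|---|---|---|
| 20 | 0.053 to 0.070 | 0.070 to 0.180 |
| 34 | 0.056 to 0.086 | 0.086 to 0.284 |

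**6. After the fix**
If pairs must have a baseline mammogram at least 8 weeks after the last systemic hormone, the on-hormone part of the window is 0 weeks and the f × d term is 0.

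**The case against.** The strongest reply is that the endpoint is minor. Density is exploratory, is not named in 8.2, and is read by Volpara only when imaging is at KUMC. Section 13.4 says the study is not powered for favourable biomarker change and promises caution in interpretation. Part of the aim is to compare two methods on the same images, and an on-hormone image enters both readings. All of this stands and limits the weight of the point. It does not close the gap, because 13.4 still tests the change itself.

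The second reply is that the size is unsupported. The documents give no share of recent hormone users, and 2.1 describes providers as reluctant to prescribe these hormones to women at increased risk. They give no data on density after stopping. The figures in 2.5 are for % density and not the Volpara scale. The 12- and 20-month intervals stack every maximum. This also stands, so the figures above are a range under assumptions.

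Two stronger readings are tempting. A reader might infer that the bias matches or exceeds the effect the trial seeks. The documents state no effect sought, and the 0.05 to 0.41% in 2.5 is a past result and not a target. A reader might also infer that the rule against "Taken tamoxifen, raloxifene, or an aromatase inhibitor within the past 6 months" has the same fault. It does not: a 6-month exclusion and a 6-month mammogram window meet only at the edge. Section 2.5 says raloxifene and exemestane do not modulate density, and recovery after tamoxifen would bias the other way.

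Finally, 8 weeks is borrowed from the RPFNA rule. Nothing in the documents shows that density settles in that time.

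**Conclusion.** The gap is real on the text. The washout protects the aspirate and not the mammogram, the mammogram can be up to about 12 months older than the first tablet, and the single-arm paired test has no rule for either. An observed fall in density could not be attributed to Duavee on the analysis as written.

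The size of the bias is not known. The -0.2 to -0.6 points rests on an assumed 10 to 30% share of on-hormone baselines, prior combined therapy, full reversal and the % density scale. The untreated decline of up to 0.3 points before the first tablet rests on the plan's placebo figure, a linear course and the longest allowed gap.

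The consequence is confined to the exploratory density endpoint. Accrual and retention do not depend on it, and Ki-67 has its own washout. It is worth correcting because the correction is cheap and the pilot is meant to inform a larger trial.

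**What to change.** In 13.4:
- Record the date of the last systemic hormone relative to the baseline mammogram.
- Base the density-change analysis, for both Volpara and Cumulus, on pairs whose baseline mammogram was at least 8 weeks after that date. Show all pairs as a sensitivity analysis.
- Report the distribution of the interval from baseline mammogram to first tablet and of the interval between mammograms.
- Set the Cumulus % density change, and only that one, against the plan's placebo decline of about 0.3% per 12 months, scaled to the observed interval. Make no such comparison for Volpara, which is on a different scale.

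No restriction on prior SERM or aromatase inhibitor use is needed. Eligibility, visits and treatment do not change. The cost is a few fewer density pairs in the main analysis and possibly one extra data field, because 4.1.5 requires confirmation of at least 8 weeks off hormones and the protocol names no field for an exact stop date.
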